- *Potential problems with delivery of intervention:* number of incorrect phone numbers, changed phone numbers; problems with Website described by participants and staff; description of level of annoyance with outreach messages through text, phone, and Facebook; number of participants re-incarcerated during intervention trial and, thus, resulted in non-completion; problems with chat feature with health educator
- *Modifications needed to maximize implementation:* suggestions from participants about improving multimedia electronic approaches; suggestions about improving real-time assessments of knowledge
- *Perception of human interaction in intervention:* positive and negative aspects of multimedia electronic educational interventions; benefits and disadvantages to offer of community-based sessions; perceived value of human face in video/audio intervention content; advantages/disadvantages of conversation during discharge planning session for control arm

Women's health literacy and screening/risk reduction outcomes are described in Table 5 below. Items will be adapted from scales listed in Table 5.

Table 5. Women's health literacy and screening/risk reduction outcomes and instruments	
Women's health literacy (Knowledge, beliefs, self-efficacy, confidence navigating systems)	Screening/ Risk reduction
Cervix literacy Pap knowledge scale ⁴⁶ Health belief model scale for cervical cancer and Pap smear test ⁴⁷ Self-efficacy for cancer screening scale ⁴⁸ Confidence navigating health systems scale (cervix, breast, birth control, STI) ⁴	Up-to-date Pap exam or HPV co-testing Abnormal Pap follow-up HINTS cervical cancer screening questions ⁴⁹ Original SHE HPV co-testing and abnormal Pap follow-up questions ⁴
Breast literacy Knowledge, beliefs, self-efficacy items from breast cancer literacy assessment ⁵⁰	Up-to-date screening mammography (biennial) for age 50+ HINTS breast cancer screening questions ⁴⁹
Birth control literacy Contraceptive knowledge assessment ⁵¹ Beliefs about acquisition and use of contraceptive items from self-efficacy scale ⁵²	Current use of hormonal or long-acting reversible birth control method, if no menopause or sterilization BRFSS birth control questions ⁵³
Sexually transmitted infection literacy STD knowledge questionnaire ⁵⁴ Multidimensional condom attitudes scale ⁵⁵ Condom self-efficacy scale ⁵⁶	Condom use at last sex STI treatment BRFSS condom use and STI treatment questions ⁵³

Data collection. Aim 1 feasibility data will be collected by study staff who have training and experience conducting qualitative interviews. Staff will conduct 30- to 60-minute key stakeholder interviews with selected

research participants. If the staff collecting data have not reached thematic saturation at a certain time point (after reviewing findings with the PI on a weekly basis), particularly with research participants, they will recruit additional key stakeholders for interviews until saturation is reached.

A record of intervention uptake and outreach using a Redcap relational database system. The project director has been using Redcap to monitor intervention uptake and outreach for the last four years as part of her duties on the original SHE study, and will employ a similar method for the present study. Some elements of data capture will occur through study staff entering data directly into Redcap, as well as auto-population of fields with a connection to the SHE-Women Website.

Aim 1 pilot and Aim 2 RCT effectiveness outcomes data will be collected in surveys at baseline and post-intervention for Aim 1, and then also at 1, 2, and 3 years for Aim 2. For Aim 1, depending on the method of re-consenting original SHE participants (over the phone or in person), study staff will conduct the baseline assessment either over the phone or in person using a Web link on the SHE-Women study Website. The Web link to the survey will utilize audio computer-assisted self-interview (ACASI) technology, where the computer device will read the questions and answer options aloud as participants move through the assessment. Study staff will make themselves available in person or by phone to guide participants through the Web survey, if they desire this service. Participants will have the option to turn off audio if they cannot gain access to headphones or are in a public place. To facilitate use of ACASI, participants will be offered free headphones at study start, and then at quarterly check-ins, or follow-up surveys. We have used ACASI with other hard to reach low literacy populations with success (active drug users and with women leaving corrections in other cities). For the Aim 2 RCT, study staff will conduct the baseline assessment using the same Web link to the SHE-Women study Website so that participants become accustomed to survey administration using a secure Web link. Participants randomized to the control arm will not have access to any intervention content on the Website. All other surveys – post-intervention, and 1-, 2-, and 3-year follow-up surveys, will be administered using the same Web link to an ACASI-administered survey. Participants will always be given the option of completing the survey over the phone or in person with a member of the study staff, if that is their preference. If participants become re-incarcerated during the longitudinal follow-up, we can conduct surveys in person or through the mail with paper and pencil copies of the survey – we have previously employed these techniques.

Aim 3 perceptions and uptake data will be collected using the same methods described above for Aim 1.

Validation strategies. Validation of data collected is an important aspect of rigorous outcomes assessment, especially since our primary outcomes of women's health literacy and screening/risk reduction are self-reported (see Table 5). In our original SHE study, we conducted a formalized evaluation of the accuracy of self-reported cancer screening with a subsample of women.⁵⁷ We found that 61% of Pap screening self-reports were accurate against medical record review. Importantly, Pap knowledge scores and semi-structured interview assessment of Pap events were statistically significantly associated with accurate Pap screening self-report. Thus, the conclusion of our validation study in SHE, was to analyze self-reported data for a weight for Pap knowledge scores and/or semi-structured interview assessment of Pap events (a total of four questions). For the purposes of the present study, for each outcome variable in Aim 1 (cervical, breast screening, birth control, and STI screening), we will weight self-reported data for knowledge scores in each of the domains of interest (cervix, breast, birth control, and STI knowledge).

To validate data collected in key stakeholder interviews, we will rely on reaching participant or thematic saturation.⁵⁸ We will interview a subsample of participants and will continue interviewing until we have reached thematic saturation, which will be determined by the study team and the PI, who has extensive expertise in qualitative methods in both research and implementation studies.

Data analysis. For analyses of qualitative data from key stakeholder interviews in Aim 1 and Aim 3, open coding will be used to delineate conceptual categories for each transcription using an iterative process, initial codes will inform subsequent data analysis.⁵⁸ During data review meetings and after collection of data, the research associate and PI will develop a list of preliminary codes to create a codebook for subsequent analyses. Each of these two researchers will read through the rest of the transcripts and open-code each transcript independently. Coded transcripts will be checked for degree of agreement among coders, and disagreements will be resolved through discussion. Dominant themes will be extracted from these coded transcripts and guided by domains of interest in our study of feasibility and perception of human interaction in intervention (barriers and facilitators of implementation, problems with delivery of intervention, modifications needed to maximize implementation, perception of human interaction). For quantitative data in Aim 1 and Aim 3 related to the uptake of intervention components, we will summarize outcome measures with descriptive statistics.

Using quantitative data from the pilot trial of the SHE-Women text-Web intervention, we will conduct descriptive analysis and bivariate tests to explore women's health literacy (knowledge, beliefs, and self-efficacy) for screening related to cervical, breast cancer, birth control, and STIs (Aim 1). The results including effect sizes estimated for the outcome will be utilized for refinement of the intervention content and modality. To test the hypothesis that SHE-Women will be more effective than standard of care at improving outcomes (Aim 2), we will utilize mixed modeling techniques for repeated measures, separately for each outcome variable: health literacy for screening and screening/risk reduction practices. General/generalized models will evaluate the effects of the intervention by estimating overall group difference across measurements (i.e., group effect), change over time (i.e., time effect), and group difference in change (i.e., group-by-time interaction). In other words, we will evaluate whether the intervention vs. control group improves in outcomes over time. The models will account for the impacts of sociodemographic characteristics as well as other cross-cutting risk factors including tobacco use, alcohol use, criminal justice involvement, intimate partner violence, lack of continuous health care coverage or primary care contact, etc. (covariates), thereby providing unbiased estimates of the intervention effects. The models for screening/risk reduction behaviors will also consider knowledge about cervix cancer, breast cancer, birth control, or STI as an additional covariate for the respective outcome variable. Incorporating participant tracking data, descriptive analysis and bivariate tests will demonstrate the pattern and uptake of various intervention components as measured by number of participants who responded to text messages; clicks on the Website; interactive clicks on the Website, e.g. through real-time assessment of knowledge; time elapsed between text messages and Website clicks; number of outreach messages (through text, phone, or Facebook); Facebook posts/messages; chats with health educator; total minutes of contact through text, Web, chat, Facebook with each participant; and attendance at community sessions (Aim 3). General/generalized mixed modeling for repeated measures will assess the impacts of the uptake on each outcome variable of health literacy for screening and screening/risk reduction practices while controlling for the impact of sociodemographic characteristics and other risk factors. A proper covariance structure for repeated measures will be chosen for each outcome variable based on model fit (i.e., likelihood, Akaike Information Criterion, adjusted Bayesian Information Criterion). Statistical significance will be determined at 0.05 alpha level, and all analyses conducted using SAS 9.4⁵⁹

Missing data will be handled by iterative Markov Chain Monte Carlo (MCMC) multiple imputation, in which expectation-maximization (EM) algorithm provides prior estimates of missing values for subsequent MCMC procedure.⁶⁰ A large number of (e.g., 200) imputed datasets will be generated and then analysis results from each imputed dataset will be combined together to make valid statistical inference. This approach includes all selected variables (auxiliary variables) into the imputation process, which allows for greater recovery of missing data.⁶¹ It is possible that some women will reenter the jail facility during the recruitment period. To avoid re-randomizing these same participants, we will collect basic identifying information recruitment (name, DOB, race) and double check to see if the participant already is enrolled in our study.

Integration of study aims to meet project objective. Because the objective of this study is to ultimately create a sustainable model for dissemination of health promotion interventions for vulnerable populations, we feel it is important to use a mixed methods approach to understand the relationship between qualitative and quantitative data.⁶² Integration of study aims to meet our project objective will primarily occur through the writing of Manuscripts # 1,6 and 8 (see Table 3). In each of these manuscripts we plan to report on both the perceptions of key stakeholders, as well as the effectiveness of the intervention given the electronic modality of delivery. We will take lessons learned to develop subsequent projects that test SHE-Women in diverse groups of high risk women both inside and outside our catchment area.

Strategies for success, alternatives, key findings. Strategies for success include allowing for sufficient time for recruitment early in the study in case recruitment is slow, but we also draw on our successful and effective methods of recruitment, intervention delivery, and retention strategies. The integrated, mediated electronic women's health literacy intervention via text-Web delivery platform is based on carefully collected data over the last three years about use of electronic technologies among women leaving jails and extensive experience among our health communications team of developing electronic interventions. Alternative strategies in case we have problems include: having adequate time for recruitment of more participants. If we have higher than expected rates of attrition, we have adequate time, resources, and partnerships with the jails to recruit more participants. We will also leave sufficient lead time for development of the text-Web modality. We realize our methods may not allow for an ideal unbiased experimental design given convenience sampling; however, we feel that our unique access to a difficult to reach and understudied population of *prisoners* outweighs the pitfalls of utilizing convenience samples. If our hypotheses are not supported, subsequent projects will focus on discharge planning or going back to tried and true methods of face-to-face health education. Key findings from

this study will include whether a women's health literacy intervention is effective at changing intersecting behaviors among women leaving jail; whether an electronic women's health literacy intervention is feasible and effective; and how much human "touch" is ideal in an electronic intervention. Knowledge gained from this study will help develop a new paradigm for mitigating health disparities among vulnerable women.

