
 Finalize IRB protocol/approvals Finalize build out of expanded intervention content/ text-Web platform Re-consent N~20 women in original SHE cervix study to participate in SHE-Women via text-Web platform/ deliver SHE-Women Conduct stakeholder interviews with participants of SHE-Women pilot Conduct baseline, post-intervention assessment of women's health literacy outcomes Refine intervention content/text-Web platform for Aim 2 RCT 	
 Uptake of components Barriers and facilitators of implementation Problems with delivery Modifications needed Women's health literacy: knowledge, beliefs, self-efficacy for cervical, breast cancer, birth control, STI screening Increase in health literacy and self-efficacy for avoiding COVID-19 	
 IRB approval secured prior to study start Intervention content build out and text-Web platform ready by Y1Q3 Re-consent and deliver SHE-Women to N~50 original SHE participants from Y1Q3-Y1Q4 Key stakeholder interviews conducted between Y1Q3-Y1Q4 Refine intervention content and text-Web platform for Aim 2 RCT by Y1Q4 Manuscript #1 mixed methods pilot study to modify an electronic intervention for women leaving jail in Y1
Aim 2. Test the effectiveness of SHE-Women on women's health literacy, screening, and risk reduction practices against a standard of care discharge planning session using a randomized controlled trial.		

 Recruit N~200 women leaving jails, women in community organizations that cater to our 	
 Women's health literacy 	
 Recruit, consent, and deliver intervention and control arms to N~200 women between Y2Q1-Y3Q4

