
organizations (i.e. transitional living facilities, DV shelters, social support centers, etc.)
 
 • Randomize participants to intervention and control arms • Deliver SHE-Women to N~100 women via text-Web platform; deliver standard of care discharge planning session to N~100 women • Conduct baseline, post-intervention, 1, 2, 3 year assessments of women's health literacy and screening/risk reduction outcomes • Conduct N~30 stakeholder interviews to determine efficacy of COVID-19 module 	
 • Screening/risk reduction for cervical, breast cancer, unintended pregnancy, STIs and COVID-19 	
 • Manuscript #2 strategies for recruiting women leaving jails into health promotion interventions in Y3 • Conduct follow-ups for 3 years from intervention during Y1-Y5/ maintain 75-85% follow-up rate • Manuscript #3 effectiveness of SHE-Women at improving women's health literacy in Y3 • Manuscript #4 effectiveness of SHE-Women at improving women's health screening/risk reduction in Y4 • Placement of SHE-Women on NCI Research-Tested Intervention Programs site in Y5 • Manuscript #5 3-year outcomes of interventions in Y5
---	---	--

Aim 3. Understand the role and impact of human interaction in electronic interventions by tracking participants and interviewing key stakeholders.

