Power. The sample size for the Aim 1 feasibility study is based on our original SHE study pilot and expanded to allow for rigorous testing and refining of modality.²⁶ The sample size of N~200 for the Aim 2 RCT was determined to provide satisfactory power ($\geq 80\%$) for this study in addressing the specific aims, which depends on the following parameters: number of participants (n), number of measurements (t=3 for health literacy for screening; t=4 for screening/risk reduction practices), effect size (f) as group difference in change, correlation between repeated measures (r), and attrition rate. The effect sizes estimated from the original SHE study were in the small to moderate range—for health literacy (8 domains), average $f=0.13$ at immediately post-intervention and 0.16 at 1-year post-intervention; $f=0.17$ for cervix screening and 0.12 for condom use during the last intercourse at 1-year post-intervention. Although effect sizes for breast cancer screening and STI screening are not available from the original SHE study, we expect similar, small to moderate effect sizes for these outcomes. Thus, we conservatively assumed the smallest observed effect size of $f=0.12$ for our power calculation. The correlations between repeated measures observed in the original SHE study were $r=0.46$ on average, with the range of 0.39-0.75 between baseline and immediately post-intervention and 0.25-0.61 between baseline and 1-year post-intervention. Power analysis of these data ($f=0.13$, $t=3$ or 4, $r=0.46$) and G*Power 3.1.9.2 indicated that a sample of 124 women will produce $\geq 80\%$ power for both health literacy (80%) and screening/risk reduction behaviors (85%). In our original SHE study, the 3-year follow-up rate was 85%. Conservatively assuming a high attrition rate up to 40%, we will recruit ~200 women at baseline to adequately power the SHE-Women study—i.e., maintain $\geq 80\%$ power even with a low follow-up rate as small as 60%. As

Table 4. Expected attrition over study period

	Aim 1 feasibility Target N~20	Aim 2 RCT Target N~200	Aim 3 (same as Aim 2)
Consent and baseline	20	260	--
Intervention initiation	15	220	--
Post-intervention	10	200	--
1 year follow-up	--	170	--
2-year follow-up	--	160	--
3-year follow-up	--	150	--

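### Screening/risk reduction has an effectiveness paper in Year 4, before any 3-year visit can exist, and a 3-year paper in Year 5, both under 0.05, with no statement of which analysis decides

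*Combined protocol and SAP*

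**What the plan says.** - **Outcome.** The Overview of study and the Outcomes and instruments section place screening/risk reduction at 1, 2 and 3 years after the intervention. The Overview adds that follow-up finishes by Year 5.
- **Enrolment.** Table 3, Aim 2: "Recruit, consent, and deliver intervention and control arms to N~200 women between Y2Q1-Y3Q4". The recruitment section expects accrual to take one year and allows two.
- **Reporting.** Among the Aim 2 benchmarks in Table 3, Manuscript #4 is to report the "effectiveness of SHE-Women at improving women's health screening/risk reduction in Y4" and Manuscript #5 the "3-year outcomes of interventions in Y5". Manuscript #3, on literacy effectiveness, is due in Year 3.
- **Analysis.** The Data analysis section gives one repeated-measures mixed model per outcome, which estimates among other effects the "group difference in change (i.e., group-by-time interaction". On the threshold: "Statistical significance will be determined at 0.05 alpha level".
- **Power.** The Power section counts "t=4 for screening/risk reduction practices" and reports that 124 women give 80% power for literacy and 85% for screening/risk reduction.

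The documents name no primary time point, no interim-analysis plan and no division of alpha. They also do not say which visits Manuscript #4 will use.

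**The concern.** The paper labelled as the effectiveness paper for screening/risk reduction comes out before the analysis that was powered can be run. A Year 5 paper then returns to the same outcome with more follow-up, at the same 0.05. A claim of effectiveness could therefore rest on either of two overlapping analyses, and the two could disagree with no rule for which one stands. Table 3 lists these papers as benchmarks for success, beside placement of the intervention on a national register of research-tested programmes in Year 5. A Year 4 claim could support that listing before the four-visit data are complete. A reader may also carry the 85% over to the Year 4 result, although it was calculated for a different data set.

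**Working it through.** **1. Calendar (Table 3 and the recruitment section).** A woman treated in quarter q reaches her k-year visit k years later.

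| Treated in | 1 year | 2 years | 3 years |
|---|---|---|---|
| Y2Q1 (first possible) | Y3Q1 | Y4Q1 | Y5Q1 |
| Y2Q4 (end of one-year accrual) | Y3Q4 | Y4Q4 | Y5Q4 |
| Y3Q4 (end of permitted window) | Y4Q4 | Y5Q4 | Y6Q4 |

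No 3-year visit exists in Year 4 on any accrual path. The four-visit data are complete by the end of Year 5 only if accrual ends in Year 2. Under the two-year window, women treated in Year 3 have no 3-year visit by then. For literacy, a woman treated in Y3Q4 has her 1-year visit in Y4Q4, after Manuscript #3 is due.

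**2. The plan's own power figure.** I used the G*Power repeated-measures within-between interaction: λ = f²·N·t/(1−r), df1 = t−1, df2 = (N−2)(t−1), alpha 0.05. Inputs from the Power section are N=124 and r=0.46. The section says "we conservatively assumed the smallest observed effect size of $f=0.12$ for our power calculation", but the run it prints uses f=0.13.
- f=0.12, t=3: λ = 0.0144×124×3/0.54 = 9.92, power 80.7% (stated 80%).
- f=0.12, t=4: λ = 0.0144×124×4/0.54 = 13.23, power 87.3% (stated 85%; 2.3 points higher). Multivariate degrees of freedom give 86.5%.
- f=0.13: 86.9% and 92.4%, so the printed value reproduces neither figure.

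I use f=0.12 below because it comes closer.

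**3. Power of a Year 4 test, same formula, f=0.12, r=0.46.**

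| N | t=2 (baseline, 1 year) | t=3 (baseline, 1, 2 years) |
|---|---|---|
| 124 | 72% | 81% |
| 160 (Table 4, 2 years) | 83% | 90% |
| 170 (Table 4, 1 year) | 85% | 92% |

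Matching each test to its own Table 4 number gives 85% (t=2, N=170) and 90% (t=3, N=160).

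**4. False-positive rate over two looks.** I simulated arm differences at four visits under the null, with exchangeable correlation, complete data and large-sample Wald tests at 0.05 at each look. The rate is P(Year 4 test significant or Year 5 test significant).
- Group-by-time, Year 4 on baseline and 1 year, Year 5 on four visits: 8.1%.
- Group-by-time, Year 4 on baseline, 1 and 2 years, Year 5 on four visits: 7.0%.
- Group-by-time with entry staggered over two years: about 7.9%.
- Year 4 on the 1-year change, Year 5 on the 3-year change alone: 9.1%.
- Other choices: overall group effect 6.2-7.0% (r=0.46), contrast with the mean of the follow-up visits 6.6-7.7%, linear trend 8.6-9.5%.
- Ceiling for two independent tests: 1 − 0.95² = 9.75%.

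The group-by-time results are the same for r from 0.25 to 0.75. They also show how often the papers would disagree under the null: (8.1−5.0)/5.0, or about 63% of positive 1-year tests, would not be confirmed by the four-visit test. With two follow-up years it is (7.0−5.0)/5.0, or about 39%.

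**5. A strict Year 4 threshold.** With known variance and complete data, the four-visit statistic is never smaller than the two-visit statistic nested in it. The chi-square(1) critical value at 0.005 is 7.88, above the chi-square(3) value of 7.81 at 0.05. A Year 4 pass at 0.005 therefore implies a Year 5 pass at 0.05, and the overall rate stays at 5.0%. If Year 5 tested the 3-year change alone, it would be about 5.3%.

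**The case against.** The strongest reply is that two formal tests are inferred from two manuscript titles. The Data analysis section describes one model per outcome. Nothing says that Manuscript #5 repeats the test in #4, or that success in either is enough. Assessment at 1, 2 and 3 years is prespecified, so staged reporting may simply follow the visits, and no stopping or design change hangs on the Year 4 paper. This stands, and it makes the 7-8% conditional. It does not supply the missing statement of which analysis decides.

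A reader might infer that the Year 4 test is underpowered. The documents do not support that. The 72% and 81% apply at N=124, the number that allows for attrition of up to 40%. At Table 4's expected numbers the Year 4 test is at or above 85%.

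A reader might also infer that Year 4 must be a look at partly accrued data. It need not be: even with enrolment to Y3Q4 all 1-year visits fall due by Y4Q4, and with one-year accrual all 2-year visits do too. With one-year accrual the literacy timing problem also largely disappears. Finally, the excess error is modest, at about 2-3 percentage points per outcome for the planned test.

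**Conclusion.** The point holds as a gap in the plan. An effectiveness paper is scheduled when the powered four-visit analysis cannot exist, a second paper on the same outcome follows a year later, both fall under 0.05, and no deciding analysis is named. The size is about 7-8% per outcome for the group-by-time test, or about 6-9.5% over other reasonable tests. These are not figures from the documents. They assume that both papers test, that either result counts, exchangeable correlation and complete data, whereas the plan will use multiple imputation.

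The 85% describes the t=4 analysis only. For Year 4 the corresponding power at f=0.12 and r=0.46 is about 85-90% with expected retention, and 72% (t=2) or 81% (t=3) at N=124. It would be wrong to read the documents as stating that effectiveness will be declared twice, or that a Year 5 analysis will necessarily hold every woman's 3-year visit. The latter is true only if accrual ends in Year 2.

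**What to change.** 1. In Data analysis, name the four-visit group-by-time test (baseline, 1, 2 and 3 years) as the single confirmatory analysis of each screening/risk-reduction outcome at 0.05, run once the last enrolled woman's 3-year window has closed.
2. Reconcile the Y3Q4 enrolment limit with finishing follow-up by Year 5: either close accrual in Year 2, or move the confirmatory analysis to after Year 5.
3. In Table 3, label Manuscript #4 as interim, state which visits it uses, and limit it to estimates and confidence intervals. If a Year 4 claim is wanted, set a strict threshold such as p<0.005 and keep 0.05 for the four-visit test. The overall rate is then about 5.0%, on the complete-data assumption.
4. In Power, say that the 85% refers to the four-visit test, and settle whether f is 0.12 or 0.13.
5. If recruitment runs into Year 3, hold the literacy effectiveness test until all 1-year windows have closed.

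These are wording changes with no new visits or data, although item 2 may shorten accrual or lengthen the study. The downside is that a formal effectiveness claim may come a year or more later, or must meet a stricter threshold in Year 4.
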